 2. Baseline measures and information will be collected from patient and medical record which include demographic information including gender, DOB, height, weight, co-morbidities, prior level of function, medical complications or concerns (pressure injuries, falls etc), precautions, admission level of function based on QI mobility items

STU#: 00216223

and outcomes measures in electronic medical record, reason for admission to rehabilitation.

3. Intervention:

1. Group and individual physical or occupational therapy sessions that are focused on endurance training (using upper and/or lower limb activities) which is a part of standard care for appropriate patients.
2. The only addition to usual standard care is the addition of a HR monitor that syncs with the Heart Zones software platform with or without visual feedback. Subjects will wear the HR monitor on their less sensory/motor impaired upper extremity.
3. There will be a continuous rolling enrollment, so some participants will receive HR feedback first while others will receive it on their second week.
4. Timing
 - i. Inpatient: 1 week of visual feedback of HR during group sessions and 1 week they will receive no feedback on their HR/zones.
 - ii. Day rehabilitation or community fitness: 2 weeks of visual feedback of HR and 2 weeks of no feedback due to fewer sessions per week.
5. Session Monitoring and Feedback
 - i. We will ask participants to rate their level of perceived exertion by using the Borg RPE Scale (6-20) at baseline, mid, and post each group session.
 - ii. Participants will answer 2 self-efficacy and confidence questions at the end of each session, rated from 0-100%.
 - iii. Subject's HR data from each session will be transferred for storage on a password protected computer accessible by approved lab staff only in order to perform summative data analysis, including peak HR, time in target HR zone, and average HR for whole session and for endurance training portion of the session.
6. We will monitor for occurrence of adverse events during sessions by assessing physiologic response to exercise, incidence of falls, etc.

4. Midpoint

1. We will collect information from their electronic medical record including new medical complications or concerns, their current functional level based on QI mobility items and outcome measures completed.

5. Post

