1. At the end of the study, we will ask participants to answer one summative quality improvement question regarding their participation in the study.
 - i. If discharged unexpectedly, we will attempt to reach out to participants via their preferred contact method (phone or email) in order to allow them to provide feedback.
2. We will collect information from their electronic medical record including new medical complications or concerns, their current functional level based on QI mobility items and outcome measures completed and ask the participant regarding discharge destination.
3. If the submax exercise test was completed at baseline, we will complete the same test a second time at least 3 days later.

AIM 6:

- a. We will ask for provider feedback and perceptions at the end of the study by their completion of the Acceptability, Appropriateness and Feasibility Questionnaire.
- b. Given the potential for covering providers, we will only ask participation from participating providers who are core staff/covering for a long term placement at each of the study locations.

STU#: 00216223

SHARING RESULTS WITH PARTICIPANTS

Given the nature of the study design, participants will receive immediate continuous feedback of their heartrate for a portion of the study. Individual study results may be provided once the study is completed if the patient requests. Results will be shared in written or verbal means, depending on participant's preference.

STUDY TIMELINES

The participant will be in the study for up to the duration of their length of stay in inpatient rehabilitation or day rehabilitation. We anticipate that it will take up to 8 months to enroll all study participants and primary analyses will be completed by September 2022.

INCLUSION AND EXCLUSION CRITERIA

Participant Criteria:

Inclusion:

- Age 18-90 years
- Admitted to inpatient rehabilitation, day rehabilitation or participant in community fitness
- Qualifies for group therapy based on diagnosis and insurance reimbursement
- Physician clearance for participation

Exclusion:

- Unable to provide informed consent due to cognitive impairment
- Inability to communicate with investigators
- Sternal Precautions
- Individuals with LVADs
- Pregnant women
- Uncontrolled Hypertension
- Serious and unstable cardiac arrhythmias
- Loss of bilateral upper extremity sensation
- At high risk for skin breakdown due to poor skin integrity (open wound, fragile skin, etc)

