Participants may be withdrawn from the study without their consent if they are transferred to the MACU for higher level monitoring or discharged from rehabilitation care due to acute hospitalization for a change in medical status lasting greater than 72 hours or if they no longer meet inclusion criteria for the study.

RISKS TO PARTICIPANTS

The possible adverse events or risks from the study procedures may include, but are not limited to:

- Discomfort or pressure caused by armband: temporary, minor risk associated with direct usage during the session. Adjustment will be provided if patient provides feedback that it is too tight.

STU#: 00216223

- Risk of skin breakdown due to armband pressure will be minimized by excluding people with sensory loss. Adjustments will be provided if the patient provides feedback regarding discomfort. If redness lasts greater 15 minutes after the session, patient may be placed on hold from further study participation at the discretion of the research PT and clinical teams.
- Fatigue, or Muscle Soreness: these risks are associated with usual care and are associated with exercise. We do not anticipate an increased incidence of these occurring due to participation in this study. To minimize this risk, subjects will be closely monitored throughout sessions by their provider and given rest breaks as needed.
- Chest Pain or Shortness of Breath: this is a potential risk of exercise, particularly for those with underlying medical conditions. We do not anticipate an increased incidence of this occurring due to participation in this study. To minimize this risk, subjects will be closely monitored throughout the sessions by their provider and provided rest breaks as needed.
- Falls: this risk is associated with participation in exercise and is not increased by use of the heart monitor. To minimize this risk, participants may be asked to wear a gait belt around the waist or a harness for safety or use an assistive device like a cane or walker per the discretion of the PT/OT/exercise physiologist.
- Loss of confidentiality of HR Intensity: because this study involves using HR in a group setting with feedback, the participants' HRs and zones will be viewable to other participants of the group. Subjects will be able to self-identify/choose a nickname for the monitor during group training.

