- Risk of loss of confidentiality will be minimized by not including personal identifying information on forms (participant will be assigned a research study number) and by conducting data collection in a private setting.

POTENTIAL BENEFITS TO PARTICIPANTS

There is likely no direct benefit to participants. Participation in this study will help researchers understanding if the use of visual feedback of HR in a group setting is feasible, efficacious and acceptable as care provided in a group model is a standard in rehabilitation.

DATA MANAGEMENT AND CONFIDENTIALITY

The analytic plan follows from the aims and the hypotheses. Descriptive statistics will be used to describe the participants and the data. Statistical tests will be utilized to assess for differences in individual outcomes baseline, mid and post through paired t-tests or appropriate non-parametric tests in consultation with a statistician. Data regarding the aims below may be analyzed for group sessions, individual sessions, and combined.

Aim 1: The null hypothesis is that there is no different in therapist behaviors to monitor/progress intensity prior to study, without visual feedback, or with visual feedback of participant's HR.

Aim 2: The null hypothesis is that there will be no difference in participant's ability to reach target intensity between sessions in which visual feedback of HR is provided and sessions where there is no visual feedback.

Aim 3: The null hypothesis is that there will be no increase in number of adverse events related to the use of Heart Zones with and without visual feedback.

Aim 4: The null hypothesis is that there will be no difference in participant exercise self-efficacy and confidence in reaching appropriate intensity when using visual feedback to no visual feedback during sessions.

Aim 5: The null hypothesis is that there will be no difference between submax exercise tests completed at baseline compared to post.

STU#: 00216223

Aim 6: The null hypothesis is that the providers will not feel the technology is appropriate, acceptable or feasible to use in a rehabilitation setting.

Data will be transferred to and stored on Shirley Ryan AbilityLab's REDCap system.

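### The Aim 3 feedback contrast is uninformative about armband harm because the band is worn in both conditions, and the post-session redness trigger has no planned observation behind it

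*Combined protocol and SAP*

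**What the plan says.** All references are to the combined protocol and SAP.

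- **What is added to care** (Procedures Involved, Aims 2-5, Intervention, item 2): "The only addition to usual standard care is the addition of a HR monitor that syncs with the Heart Zones software platform". This applies whether or not the display is shown to participants. The same item places the monitor on whichever arm has less sensory or motor impairment.
- **Safety monitoring** (Intervention, item 6): "We will monitor for occurrence of adverse events during sessions by assessing physiologic response to exercise, incidence of falls, etc".
- **Chart review** (Midpoint and Post): "We will collect information from their electronic medical record including new medical complications or concerns". The corresponding baseline item shows that this category includes pressure injuries.
- **Skin trigger** (Risks to Participants): "If redness lasts greater 15 minutes after the session, patient may be placed on hold from further study participation". The hold is at the discretion of the research physical therapist and the clinical teams.
- **Stated safeguard** (Risks to Participants): "Risk of skin breakdown due to armband pressure will be minimized by excluding people with sensory loss".
- **Matching exclusion** (Inclusion and Exclusion Criteria): "Loss of bilateral upper extremity sensation".
- **Aim 3 null hypothesis** (Data Management and Confidentiality): "no increase in number of adverse events related to the use of Heart Zones with and without visual feedback".
- **Safety endpoint** (Study Endpoints): the recorded incidence of adverse events, with no comparator named.

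**The concern.** Aim 3 sets out to determine whether using the Heart Zones technology in rehabilitation is safe. The monitor is the only stated addition to usual-care sessions, but the one comparison set out for Aim 3 is between two periods in which it is worn alike. A null result there could be read as evidence that the armband is harmless, which it is not.

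The incidence endpoint does not have this limitation, but it depends on events being observed. The plan's own skin trigger refers to a time after the session, while its stated monitoring is during the session. If nobody is assigned to look or to record, a count of zero cannot be told apart from not having looked.

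The safeguard offered for skin risk is also described more broadly in the Risks section than the eligibility criteria deliver.

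**Working it through.** The plan gives no adverse-event rate, margin, alpha or power for Aim 3, so there is no figure of its own to reproduce. The rates and the 5% level below are assumptions. The sample size of 90 completers is the plan's.

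**1. Is the band worn in both conditions?** Yes. Intervention item 2 has the monitor on with or without feedback, and Aim 1 Conditions 2 and 3 both have it on. The only no-monitor condition, Aim 1 Condition 1, counts provider behaviours and no adverse events.

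**2. What can the contrast show?** If feedback does not alter armband risk, the expected difference between periods is zero whatever that risk is. This follows directly from step 1. The table gives rejection rates for an exact two-sided McNemar test with n = 90, alpha = 0.05, equal risk q in each period and independent periods.

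| q per period | Rejection rate |
|---|---|
| 1% | 0.0003 |
| 2% | 0.0035 |
| 5% | 0.0196 |
| 10% | 0.0283 |
| 20% | 0.0304 |

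The rate never exceeds the nominal level, so the test has no power for armband harm. If harder exercise did change skin risk, the contrast would estimate that increment and still not the band's own risk.

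**3. What can incidence show, if events are recorded?** The chance of at least one event in 90 is 1 − (1 − p)^90:
- p = 1%: 59.5%
- p = 2%: 83.8%
- p = 5%: 99.0%

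Exact limits:
- 0/90, one-sided 95% upper bound: 1 − 0.05^(1/90) = 3.3%
- 0/90, two-sided 95% upper limit: 1 − 0.025^(1/90) = 4.0%
- 3/90, two-sided 95% interval: 0.7% to 9.4%

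**4. What if only a fraction s of events is captured?** Zero recorded events then bounds p × s, so the one-sided bound on p is about 3.27%/s. At s = 1 it is 3.3%, and at s = 0.5 (assumed) it is 3.27/0.5 = 6.5%. The documents give no basis for choosing s.

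**5. Trigger against monitoring window.** The trigger is timed from the end of the session. Item 6 covers the session itself and lists physiologic response and falls, then an open-ended remainder. Nothing says who checks the skin afterwards, where the finding is recorded, or whether redness counts as an adverse event. The two armband items in the Risks section make adjustment depend on the participant's own feedback.

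**6. Sensory loss.** The Risks section speaks of excluding people with sensory loss. The criteria exclude only loss in both upper extremities, and the placement rule anticipates impaired arms among those enrolled. As written, a person with partial sensory impairment in both arms could enrol.

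**The case against.** **The safety endpoint is incidence, not the contrast.** This stands. A skin event under the band can be attributed to it without a comparator, and the plan provides for descriptive statistics. A reader might infer that armband harm cannot be shown, or that a finding of no problem is guaranteed by the design. The documents do not support that; the limitation belongs to the feedback contrast.

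**The band is not the only risk.** This also stands. A reader might take the wording about the only addition to care to mean the only added risk. The Risks section separately lists loss of confidentiality from the group display, submaximal testing is a further study procedure, and feedback is intended to raise intensity.

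**Other routes exist for finding skin events.** Charts are reviewed at midpoint and post, participants must promptly notify the investigator of illness or injury, nursing staff are available around the clock, and the monitoring list is open-ended. These routes could well find pressure injuries. They are less likely to find transient redness, which is what the trigger concerns, and they are weakest where participants go home after a session. That some will have left within 15 minutes is an inference.

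**The plan disclaims evaluating the software and uses a commercial, non-invasive sensor.** A feedback contrast does fit the question about feedback. The disclaimer names the software, however, while Aim 3 speaks of the technology, so the conclusion still needs bounding.

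**Other criteria reduce skin risk.** People at high risk of skin breakdown and those unable to communicate with investigators are excluded, and placement on the less impaired arm is itself a mitigation. That lowers the risk but does not reconcile the two statements on sensory loss.

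**Conclusion.** The concern holds in a limited form. The Aim 3 feedback contrast carries no information about the armband's own risk, and a null result from it should not be reported as showing that the technology is safe. The incidence endpoint could fill that gap, but the plan describes no observation at the time its redness trigger refers to, so transient redness would probably go unrecorded unless reported or charted.

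With full recording, 90 participants with no event would exclude a per-participant risk above 3.3% (one-sided 95%) or 4.0% (two-sided). Without it, the bound is looser by an unknown factor. The contrast result assumes that feedback does not change armband risk. The table further assumes independent periods and a 5% test.

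No figure in the plan is shown to be wrong, and the expected harm is mostly minor. The 15-minute threshold and the discretionary hold are not judged here.

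**What to change.** 1. Add a yes/no armband-skin item to the data already collected at each session, in both conditions. No session form is named, but exertion ratings and two self-efficacy and confidence questions are already gathered.
2. Reconcile the during-session monitoring statement with the plan's own post-session trigger: state who observes, where it is recorded, and whether redness counts as an adverse event. An item completed only as the session ends would not by itself cover the trigger. The clinical rule need not change.
3. Reconcile the Risks statement on sensory loss with the exclusion criterion and the arm-placement rule.
4. Report armband skin events and holds as absolute incidence per participant, pooled over both periods, with an exact confidence interval. Use everyone who wore the band as the denominator, so that people put on hold are not lost from a completers-only count.
5. Reserve the feedback contrast for exercise-related events. Word the Aim 3 conclusion as the effect of feedback plus the observed incidence of armband events.

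Cost: one data item, brief extra recording per session, and protocol wording. The downside is that some mild redness will be reported that would otherwise have been missed.

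### A paired test of feedback against no feedback (Aims 2 and 4) is biased if the order split is unequal and outcomes also drift between blocks; the plan states neither an order rule nor a period adjustment

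*Combined protocol and SAP*

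**What the plan says.** All references are to the combined protocol and SAP.

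- **Tests.** The analytic plan under Data Management and Confidentiality has one sentence on testing. It names methods "to assess for differences in individual outcomes baseline, mid and post through paired t-tests or appropriate non-parametric tests in consultation with a statistician". It adds: "Data regarding the aims below may be analyzed for group sessions, individual sessions, and combined".
- **Contrast.** In the same section, the Aim 2 null hypothesis concerns a difference "between sessions in which visual feedback of HR is provided and sessions where there is no visual feedback". The Aim 4 null makes the same comparison for self-efficacy and confidence.
- **Order.** Procedures Involved, Aims 2-5, Intervention, item 3: "There will be a continuous rolling enrollment, so some participants will receive HR feedback first while others will receive it on their second week". Under Timing, inpatients have one week in each condition, and day rehabilitation and community fitness participants have two weeks in each. No washout is mentioned.
- **Outcomes.** These are collected session by session. Heart-rate data are summarised "including peak HR, time in target HR zone, and average HR for whole session and for endurance training portion of the session". For Aim 4: "Participants will answer 2 self-efficacy and confidence questions at the end of each session, rated from 0-100" percent. The Midpoint step lists medical-record items only: "We will collect information from their electronic medical record including new medical complications or concerns, their current functional level based on QI mobility items".

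No allocation rule, target ratio, balance check, period term or carryover statement appears.

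**The concern.** This is a two-block crossover in which order is a by-product of when people enter. The natural analysis, a paired test of each person's feedback block against their no-feedback block, has the right contrast. It leaves any change between the first and second block in the estimate unless the two orders are equally common.

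The participants are in active rehabilitation, so some drift is plausible. The Aim 5 hypothesis expects improvement on submaximal testing. That is indirect support only, because it concerns inpatients and a different measurement.

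If outcomes rise over time and most people have feedback first, the paired test understates the benefit, and its false findings are mainly that feedback lowers heart rate. If most have feedback second, it overstates the benefit. A falling trend swaps these directions. At stake is the study's efficacy comparison.

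**Working it through.** **Inputs from the documents.** 90 participants to complete; two blocks per person; both orders occur. There is no plan figure to reproduce: the 90 comes with no significance level, power, effect size or SD.

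**Assumed inputs.** Two-sided 5% level, SD of the within-person difference 10 bpm (within each order), drift of 1, 3 or 5 bpm, independent participants, no carryover unless stated.

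**Bias.** Take each person's difference as feedback minus no feedback.

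- Feedback first: mean tau − delta. Feedback second: mean tau + delta.
- Pooled: p(tau − delta) + (1 − p)(tau + delta) = tau + (1 − 2p)·delta.
- This is unbiased at p = 0.5 or delta = 0. With tau = 5 and delta = 3 it gives 3.8 at p = 0.7 and 6.2 at p = 0.3.

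**Period adjustment.** The second-minus-first change has mean delta + tau when feedback is second and delta − tau when it is first. Half the difference between these is tau, whatever p is.

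**False rejection, tau = 0 (40,000 simulated trials per cell).**

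| Order split | drift 1 | drift 3 | drift 5 |
|---|---|---|---|
| 50:50, paired | 5% | 4% | 3% |
| 60:40, paired | 5% | 7% | 11% |
| 70:30, paired | 7% | 18% | 39% |
| any of these, period-adjusted | 5% | 5% | 5% |

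Hand check at 70:30, drift 3:

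- Bias is −0.4 × 3 = −1.2.
- The test's SE is √(100 + 4 × 0.7 × 0.3 × 9)/√90 = 10.37/9.49 = 1.09, so it rejects beyond 1.987 × 1.09 = 2.17.
- With the split fixed, the mean varies with SD 10/√90 = 1.05. (2.17 − 1.2)/1.05 = 0.92, a tail of about 18%.

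With feedback first in 70%, nearly all of these false findings are that feedback lowers heart rate (about 18% against 0.1%). With feedback first in 30% the reverse holds.

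**How unequal might the split be?** Suppose everyone starting in the same week shares an order, and each week's order falls independently (an assumption). The recruitment statement of 2 to 3 months in each of two settings gives about 18 to 26 start weeks. The Study Timelines limit of 8 months gives about 35.

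| Start weeks | 95% range of p | average false rejection, drift 1 / 3 / 5 |
|---|---|---|
| 18 | 0.26 to 0.76 | 6 / 10 / 17% |
| 26 | 0.28 to 0.71 | 5 / 8 / 13% |
| 35 | 0.31 to 0.70 | 5 / 7 / 11% |

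If weeks alternate, p stays at about 0.4 to 0.6 and false rejection at about 5 to 6% for every drift.

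**Bounded outcomes.** Take time in zone with about a third of values at zero (assumed), p = 0.7 and latent shifts of 3, 5 and 8 points. A signed-rank test by condition rejects in 8, 12 and 22% of trials. A rank-sum test of second-minus-first differences between orders rejects in 5% each time.

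**Precision without drift.** The adjusted SE is (10/2)·√(1/n1 + 1/n2); the unadjusted SE is 10/√90 = 1.05.

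- 50:50 (45, 45): 1.05, no cost.
- 70:30 (63, 27): 1.15, about 9% larger.
- 80:20 (72, 18): 1.32, about 25% larger.

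**Carryover.** Let an amount c persist into a no-feedback block that follows feedback. The adjusted estimate becomes tau − c/2 and the unadjusted one tau + (1 − 2p)·delta − p·c. With tau = 5, delta = 3 and c = 2, the adjusted estimate is 4.0 at any split. The unadjusted one is 5.6, 4.0 and 2.4 at p = 0.3, 0.5 and 0.7.

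**The case against.** A reader might infer that the plan has no test for its efficacy question, or tests the wrong contrast. The documents do not support that firmly. The analytic plan says it follows the aims and hypotheses, names paired or non-parametric tests with a statistician's input, and then lists nulls that state the feedback contrast. A paired comparison by condition is a fair reading. The time-point wording also fits other measures: the functional items, the Aim 5 retest, or exertion, which participants "rate their level of perceived exertion by using the Borg RPE Scale (6-20) at baseline, mid, and post each group session". Taken alone, the unassigned test is only missing detail.

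A reader might also infer that an unequal order split is enough to bias the result, or that the result will be materially biased. Neither follows. Drift is needed as well, and the documents give no size or sign for it. Drifts of 3 to 5 bpm are assumptions; at 1 bpm the distortion is slight. A 70:30 split lies near the edge of the ranges above, and the order sentence is compatible with an alternating calendar, which would nearly remove the problem.

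Nor is adjustment better in every case: in the carryover example at p = 0.3, the unadjusted 5.6 is closer to the true 5 than the adjusted 4.0. There the two biases partly offset by chance, which is no reason to prefer the unadjusted test.

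What remains is that the plan does nothing to secure the balance on which the paired test relies, and says nothing of a period term that would make that balance unnecessary.

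**Conclusion.** The concern holds in limited form. It is certain that no order rule and no period adjustment are stated. The bias expression is algebra, given two blocks and no carryover. The size is unknown: zero at 50:50 or without drift, small near 60:40 with a small drift, and substantial only with a clearly unequal split and a drift of several bpm.

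The percentages rest on an assumed SD of 10 bpm, assumed drifts and independent participants. Shared group sessions could violate independence, and that was not simulated. Carryover is a separate limit. The Background cites persistence of higher-intensity time after feedback was removed, although the title of the cited study concerns auditory feedback. Period adjustment does not correct for it. The change is still worth making, because it is cheap and removes dependence on an order split that the protocol does not control.

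**What to change.** 1. Record each participant's order and report the number in each, by setting.
2. For Aims 2 and 4, name as the main analysis, before data are seen, the period-adjusted within-person contrast of block means: half the difference in mean second-minus-first change between the two orders, with a 95% CI. For skewed or bounded outcomes (time in zone, the percentage ratings), use a rank-sum test of those second-minus-first differences between orders.
3. State how order is assigned, and alternate or balance it within setting where the rolling schedule allows.
4. State carryover as a limitation that this analysis does not remove.
5. Keep the time-point paired tests for the Aim 5 retest, the functional measures and within-session exertion.

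Two sensitivity analyses are optional: a session-level mixed model, which also keeps people with only one condition, and a first-block comparison, which is between-person and imprecise.

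The cost is plan wording, one recorded variable and a little programming, with no new patients or outcome data. Balancing order is a scheduling change. Without drift, the SE rises by about 9% at 70:30 and 25% at 80:20, and not at all at 50:50. The main analysis uses only participants with both blocks, so the number with one block should be reported.
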